# 10.3 Recording of Adverse Events

## Diagnosis/Pathogenic Events and Signs and Symptoms

All AEs and SAEs should be reported. If known, the diagnosis should be recorded on the CRF rather than individual sign and symptom. However, if a series of signs and/or symptoms cannot be medically characterized as a single syndrome at the time of reporting, individual sign and/or symptom should be recorded on the CRF as AEs or SAEs. If a serious of signs and/or symptoms can be medically characterized as a single syndrome (eg, nausea and vomiting), the most medically significant sign and/or symptom should be reported as an AE, and other signs and/or symptoms should be recorded in the Additional Case Details of the CRF. If a diagnosis is subsequently confirmed, the event term should be updated to reflect the medical diagnosis.

In general, AEs secondary to other events (eg, cascade events or clinical sequelae) should be identified by the primary cause (pathogenic event) and additional sequelae should be recorded in the Additional Case Details of the CRF.

However, AEs that are temporally separate or secondary to an initial event of medical significance should be recorded on the CRF as independent events.

#### **Persistent or Recurrent Adverse Events**

A persistent AE is an ongoing extension with no resolution between assessment time points. Such events should be recorded only once on the CRF unless the severity increases. If persistent AEs become more severe, they should be recorded again on the AE page of the CRF.

Recurrent AEs are those that occur and resolve between assessment time points and subsequently recur. All recurrent AEs should be recorded on the AE page of the CRF.

### Laboratory Abnormalities

Only clinically significant laboratory abnormalities requiring active management are recorded as AE or SAE on the CRF. The criteria for clinical significance are as follows:

- Laboratory abnormalities with clinical symptoms
- Laboratory abnormalities requiring dose adjustment, interruption, or termination of the study drug
- Laboratory abnormalities requiring more frequent follow-up assessments and further diagnostic investigations, etc.
- Laboratory abnormalities requiring changes in concomitant medication, therapy, or treatment

If a clinically significant laboratory abnormality is a symptom of disease or syndrome (eg, alkaline phosphatase and bilirubin are 5 × ULN associated with cholecystitis), only the diagnosis (eg, cholecystitis) needs to be recorded on the AE page of the CRF.

If a clinically significant laboratory abnormality is not a symptom of disease or syndrome, the abnormality itself should be recorded on the CRF as an AE or SAE. Observations of the same clinically significant laboratory abnormalities at each visit should not be repeatedly recorded as AEs or SAEs on the CRF unless the severity or etiology changes.

### **Number of Deaths**

Deaths that occur during the protocol-specified AE reporting period and are attributed solely to progression by the investigator will be recorded only on the CRF. Other deaths, regardless of attribution, will be recorded on the CRF and promptly reported to the investigator.

# 10.4 Reporting of Adverse Events

All AEs and SAEs that occur between the first study-related procedures and within 30 days after the last dose of the study drug will be reported. All AEs, regardless of severity or presumed relationship to the study drug, must be recorded on the CRF using medical terms.

Refer to

(https://ctep.cancer.gov/protocolDevelopment/electronic\_applications/docs/CTCAE\_v 5\_Quick\_Reference\_5x7.pdf) for details. The investigators also need to record their opinions on the relationship between AEs and the study drug on the CRF. All actions required for AE management must be recorded in the source documents. All SAE reports must be submitted within 24 hours. For initial SAEs, all case details should be collected within 24 hours. The initial report must be as complete as possible, including details of the current diseases and SAEs, as well as an assessment of the causality between the event and the study drug. Information that is not available at the time of initial reporting (eg, end date or laboratory values of AEs) must be recorded on subsequent SAE forms when available and/or immediately upon request. The investigator must keep a copy of all SAE information on file. All SAEs that are unresolved at the time a patient discontinues study must be followed until the event is fully resolved, stabilized/sequelae resolved, or baseline (if any) is returned.

# 10.5 Data Safety

Each site shall complete the CRF and adverse reaction form or provide pictures according to the requirements of the CRF, and submit to the leading site (Institute of Hematology and Blood Diseases Hospital, Chinese Academy of Medical Sciences) for data entry and management after being reviewed by investigators. All process should be recorded.

Two independent site personnel should be responsible for data entry and management at each site. To ensure the accuracy of data, two statisticians independently enter them in duplicate and check. For queries about the CRF, the data statistician will fill in the Data Request Order (DRO) and send it to the investigator, who should promptly respond and return the DRO. Based on the investigator's response, the data statistician

will make necessary data modifications, confirmations, and entries, and send a DRO again if necessary.

A Data Safety Monitoring Committee (DSMC) consisting of at least 4 independent members (2 clinicians and 2 independent statisticians) will be established for this study. The DSMC will meet regularly to review safety and efficacy data from trials prepared by independent statisticians, and the clinician will perform interim analyses. All data presented at the meeting will be kept confidential. After each meeting, the DSMC will prepare a report and may recommend changes to the protocol.

# 11. Statistical Analysis

## 11.1 General Consideration

The statistical analyses of this study will be conducted using the statistical analysis software SAS 9.4.

Quantitative data will be statistically described using mean, standard deviation, median, maximum, and minimum. Enumeration data or grade data are expressed in terms of the number and percentage of patients.

- 1. Describe the completion of the trial, and statistically describe the excluded and dropout patients one by one.
- 2. Describe demographics and other baseline parameters.

Efficacy analysis: Summarize the data with descriptive statistics, and the main indicator is the response rate of patients, including ORR, CRR, and PR rate. The  $\chi^2$  test is used for the overall comparison, while the  $\chi^2$  partitioning method is used to correct  $\alpha$  for pairwise inter-group comparisons. Continuous variables will be presented as number, mean, standard deviation, median, and range. Discrete variables will be summarized as frequency. For time-to-event variables such as DoR to treatment, the Kaplan-Meier method is used to estimate the event occurrence rate and plot the curve. The comparison of the curves is carried out using the Log-rank method. The Cox regression model is used to analyze the influencing factors of event occurrence.

Comparisons between the 2 treatment groups are as follows: for changes of continuous variables from baseline to a specific post-baseline time point, an analysis of variance (ANOVA) is used. For discrete variables, the Cochran-Mantel-Haenszel chi-square test is used. For variables of time to onset, a stratified log-rank test is used. Except for the analysis of primary indicators, the two-sided  $\alpha$  level in other tests is 0.05. If pairwise comparisons between groups are involved.

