## 4. Study Design

## 4.1 Overall Study Design

This is a prospective multicenter Phase II clinical study employing an oral regimen administered in 3-month cycles. Patients will receive thalidomide of 50 to 100 mg QD before bedtime, prednisone of 0.5 to 1.0 mg/kg QOD, methotrexate of 10 mg/m²/week for up to 4 cycles. Prednisone will be tapered after 3 months. Patients who achieve CR can discontinue methotrexate after 4 months of consolidation therapy, with a maximum duration of 1 year. For patients who achieved a partial remission (PR) or CR, Thal maintenance therapy was recommended to be continued for a maximum duration of two years, but also depended on patients or investigator's choices.

Efficacy evaluation will be conducted at the end of each cycle starting from Cycle 1. The efficacy evaluations will continue until PD, discontinuation of treatment (for patients who continue treatment after PD), initiation of a new anti-cancer therapy, or withdrawal from the study (eg, death, patient's request, loss of follow-up, etc.), whichever occurs first.

The primary objective of this study is to evaluate the efficacy and safety of TPM regimen and further explore the biomarkers associated with clinical efficacy.

Abbreviations: CR, complete remission; MTX, methotrexate; Pred, Prednisone; Thal, thalidomide.

Notes:

Thal: 50 to 100 mg, oral, before bed, for 2 years;

Pred: 0.5-1 mg/kg, oral, every other day, could be tapered after 3 months of dosing and dosed for up to 6 months

MTX: 10 mg/m^2, once weekly, patients who achieve CR can discontinue MTX after 4 months of consolidation therapy, with a maximum duration of 1 year.

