## 4.5 Sample Size

A retrospective study of 45 patients is used as the historical control, in which cyclophosphamide monotherapy was applied with an effective rate of 72% and CRR of 47%. From the perspective of clinical expertise, taking the CRR of 70% as the minimum threshold for clinical significance, the sample size of 35 patients in this group is deemed sufficient to test the overall true CRR that is superior to that of the historical control at a false positive rate  $\alpha = 0.05$  (two sides) and false negative rate  $\beta = 0.2$  (ie, power = 80%). With a 20% dropout rate, at least 42 patients would be required to enroll in this study.

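### Section 11.1 prescribes two-group tests for a single-arm trial, and no section states the test of CRR against 47% on which the trial is sized

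*Supplement*

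**What the plan says.** All references are to protocol version 2.0; no separate SAP is shown.

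- **Design (Section 4.1).** "This is a prospective multicenter Phase II clinical study employing an oral regimen administered in 3-month cycles". All patients receive thalidomide, methotrexate and prednisone. There is no control arm, no randomisation and no stratification.
- **Sample size (Section 4.5).** "A retrospective study of 45 patients is used as the historical control", with a CRR of 47%. The calculation proceeds by "taking the CRR of 70% as the minimum threshold for clinical significance", and 35 patients are "deemed sufficient to test the overall true CRR that is superior to that of the historical control", at two-sided alpha 0.05 and 80% power. At least 42 are to be enrolled. The Synopsis gives the target as 70% to 80%.
- **Historical count (Section 2.2 table).** The 47% is 21 CRs in 45 patients.
- **General analysis (Section 11.1).** For response rates, a chi-square "test is used for the overall comparison, while the" partitioning method adjusts alpha for pairwise comparisons between groups. Then: "Comparisons between the 2 treatment groups are as follows", followed by ANOVA, Cochran-Mantel-Haenszel and stratified log-rank tests. On the level: "Except for the analysis of primary indicators, the two-sided" level elsewhere is 0.05. The paragraph ends in an unfinished sentence about pairwise comparisons.
- **Efficacy analysis (Section 11.3).** CRR and ORR are reported as point estimates with exact binomial 95% CIs. No comparison with 47% and no success criterion is given. Only the DoR, PFS and OS rules are deferred to the SAP.

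**The concern.** The methods in 11.1 are those of a trial with at least two treatment groups and strata. This trial defines neither, so the text cannot be carried out as written. The primary hypothesis behind the sample size has no stated test and no cut-off.

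That leaves the analyst to choose after the data are in. One option is a one-sample test against a fixed 47%. Another is a two-sample chi-square against the historical series, which is the only other patient group that Section 4.5 mentions. The two treat the benchmark differently: the first takes 47% as known, the second as an estimate from 45 patients. They have different cut-offs and different power, so a result a little below the 70% target could be called positive or negative depending on the choice.

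**Working it through.** **Inputs.** p0 = 0.47, p1 = 0.70, two-sided alpha 0.05, power 0.80, n = 35 analysed or 42 enrolled (Section 4.5); p1 up to 0.80 (Synopsis); historical 21/45 (Section 2.2).

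**1. The plan's own figure.** One-sample proportion, normal approximation:

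n = [(1.960·√(p0(1−p0)) + 0.842·√(p1(1−p1))) / (p1−p0)]² = [(0.978 + 0.386) / 0.23]² = 35.2.

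At n = 35, z = (0.23·√35 − 0.978) / √(0.70·0.30) = 0.835, so power is 79.8%. The stated 35 and 80% therefore come from a one-sample test against a fixed 47%.

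**2. The same test done exactly.** Reject when P(X ≥ r | n, 0.47) ≤ 0.025. This gives the same cut-offs as requiring the lower limit of the exact 95% CI to exceed 47%.

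| n | CRs needed | Lower CI limit | Upper-tail alpha | Power at 70% | Power at 80% |
|---|---|---|---|---|---|
| 35 | 23 (65.7%) | 47.8% | 0.0200 | 77.3% | 98.6% |
| 42 | 27 (64.3%) | 48.0% | 0.0182 | 83.6% | 99.5% |

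**3. The chi-square read as a two-sample test against the 45 historical patients.** For 35 v 45 at 70% v 47%, the pooled rate is (35·0.70 + 45·0.47)/80 = 0.571. The standard error of the difference is 0.1116 under the null and 0.1074 under the alternative. Then z = (0.23 − 1.960·0.1116)/0.1074 = 0.106, and power is 54.2%. Enumerating both binomial distributions gives 54.3%.

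| TPM patients | True CRR 70% | True CRR 80% |
|---|---|---|
| 35 | 54% | 87% |
| 42 | 59% | 91% |

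With a continuity correction, the figure for 35 patients at 70% falls to 46.2%; with Fisher's exact test it is 50.6%.

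**4. Where the two tests disagree.** Uncorrected chi-square against the observed 21/45:

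| Result | Exact one-sample test v 47% | Chi-square p v 21/45 |
|---|---|---|
| 23/35 | success | 0.089 |
| 24/35 | success | 0.0501 |
| 25/35 | success | 0.026 |
| 27/42 | success | 0.099 |
| 28/42 | success | 0.060 |
| 29/42 | success | 0.035 |

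The outcome depends on the test at 23–24 of 35 and at 27–28 of 42, that is, at observed rates of 64% to 69%. At a true CRR of 70%, the chance of landing in that zone is 77.3% − 51.0% = 26.3% with 35 patients, and 83.6% − 62.7% = 20.9% with 42.

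**5. How firm the 47% is.** The exact 95% CI for 21/45 is 31.7% to 62.1%. If the regimen were no better than cyclophosphamide and the true common rate were 55% or 60%, the rule of at least 23 of 35 would be met 13.4% or 30.6% of the time. This does not bear on which test 11.1 names. It bears on how the conclusion may be worded.

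**The case against.** The strongest defence is that the right elements are already present. Section 11.3, the dedicated efficacy section, gives CRR with an exact binomial CI, which is the proper single-arm summary, and Section 4.5 gives the benchmark and the level. On this view 11.1 is left-over generic text and only one sentence is missing. Much of this stands, and the fix should build on 11.3. But the two-group text is in the current protocol, and nothing says that 11.3 overrides it. The matters left to the SAP do not include the CRR test.

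Three stronger readings are tempting, and the documents do not support them.

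- *That the stated 80% power is wrong and the true figure is 54%.* The 80% is about right for the one-sample test that generates the 35. The 54% belongs to a two-sample test that the documents do not say is intended, and it holds only for a true CRR of 70% with 35 patients.
- *That a comparison with the historical series is the only chi-square available.* A one-sample chi-square against a fixed 47% is possible, and its normal-approximation form reproduces the sample size. Section 11.1 does not say what its overall comparison compares.
- *That 11.1 and 4.5 conflict on alpha.* Section 11.1 sets the primary analysis apart without giving its level, and 4.5 supplies 0.05 two-sided. The wording is loose, but the two can be read together.

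It is also fair to say that the uncertainty in the 47% applies equally to the one-sample test recommended below.

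**Conclusion.** Wrong as written. Section 11.1 specifies comparisons that a single-arm trial cannot make, and the primary hypothesis of Section 4.5 has no stated test or success rule. The sample size itself is not at fault.

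The consequence is an open choice of primary test. That choice decides the outcome at 23–24 of 35 or 27–28 of 42 CRs and, at a true CRR of 70%, separates 77% exact power from about 54% (35 patients), or 84% from about 59% (42 patients). At a true CRR of 80% the gap is smaller: 99% against 87% with 35 patients, and 99% against 91% with 42. These figures assume that the historical data enter as 21/45, that all 35 or 42 patients are in the denominator, and that the chi-square is uncorrected.

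**What to change.** Delete from Section 11.1 the chi-square partitioning and the comparisons between two treatment groups (ANOVA, Cochran-Mantel-Haenszel, stratified log-rank), including the unfinished last sentence. Put in their place:

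> Primary analysis: one-sample exact binomial test of CRR against 47%, two-sided alpha 0.05. Success is declared if the lower limit of the exact 95% CI in Section 11.3 exceeds 47% (at least 23 CRs of 35, or 27 of 42).

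In addition:

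- In Section 4.5, name the one-sample test and report its exact power at a CRR of 70%: 77.3% with 35 patients, 83.6% with 42.
- Word the conclusion as a CRR exceeding a fixed benchmark of 47%.
- Give the difference in CRR from 21/45 with its 95% CI as a supportive analysis, so that the uncertainty of the benchmark is visible.

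The cost is protocol and SAP wording; patient numbers and data collection do not change. There are two downsides: the claim is more modest than superiority to cyclophosphamide, and the stated power with 35 patients falls slightly below 80%.

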# 11.2 Safety Analysis

The safety profile will be analyzed based on AEs, physical examination, vital sign measurements, laboratory measurements, and ECG findings. AEs will be graded as per NCI CTCAE (Version 5.0).

In general, the safety analysis will be descriptive and presented in tabular form with appropriate summary statistics. The number of patients and events of hematological and non-hematological toxicity (based on NCI CTCAE Version 5.0) will be listed, and the incidence will be calculated.

# 11.3 Efficacy Analysis

The efficacy analysis will involve CRR and ORR (sum of CR and PR rates). Efficacy variables will be tabulated and summarized. For the numbers and percentages of CRR

and ORR, point estimates and 95% exact binomial CIs will be provided.

Time-to-event variables including DoR, PFS, and OS will be summarized descriptively using the Kaplan-Meier method. The rules for DoR, PFS, and OS analyses will be specified in the Statistical Analysis Plan (SAP). Growth modulation indices (intrasubject ratios of DOR, PFS, and OS, post-study treatment versus DOR, PFS, and OS post the most recent prior treatment regimen) will be summarized.

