# 8. Study Procedures

Only untreated or standard-of-care naive patients, patients with poor responses (failure to achieve PR) or relapse after receiving a non-methotrexate/thalidomide-based regimen, and patients who did not achieve PR within 4 weeks of methotrexate monotherapy can be enrolled in this study. Therefore, prior treatment and efficacy will also be evaluated before enrollment. The study consists of a screening period (Day –28 to Day 0), a treatment period, end of treatment, and a follow-up period.

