# 8.1 Screening Period

All patients will undergo study eligibility screening, which will be completed within 4 weeks before the start of the study, including:

- Review of inclusion/exclusion criteria
- Physical examinations
- Vital signs measurements (body temperature, pulse, systolic and diastolic blood pressure, and respiratory rate)
- Height, weight, and body surface area
- ECOG performance status
- Disease-related signs and symptoms
- Assessment and recording of serious pre-treatment events
- Complete medical history (previous treatment and efficacy, enlargement of liver, spleen and lymph nodes; presence of other comorbidities)
- Hematology: Hemoglobin, ANC, WBC count, platelets
- Blood chemistry: Serum glucose, AST, ALT, total bilirubin, creatinine, Na, K, uric acid, total protein, and albumin
- Serum lactate dehydrogenase (LDH)
- Serum β2 microglobulin
- Serum immunoglobulin quantification
- Serological tests for HIV, hepatitis C virus (HCV), and HBV (including hepatitis B surface antigen [HBsAg], anti- hepatitis B surface antibody [HBsAb], and anti-hepatitis B core antibody [HBcAb])
- HBV-DNA and HCV RNA: HBV-DNA and HCV RNA will be used in patients with serologically positive HBV or HCV, respectively
- Coagulation function (8 items)
- Detection of peripheral blood lymphocyte subsets (B/T/NK; Treg; T-cell immune function; TH1/TH2)

- Peripheral blood flow cytometry
- Pregnancy test (if applicable)
- Urinalysis and stool
- Bone marrow aspiration and biopsy
- Bone marrow smear, immunohistochemistry, and flow immunophenotyping
- Flow cytometry detection of LGLs in patient's bone marrow fluid or peripheral blood; flow cytometry detection of killer immunoglobulin-like receptor; TCR rearrangement; TCRvβ flow cytometry, karyotyping; next generation sequencing
- Electrocardiograph (ECG)
- Computed tomography (CT) for assessment of measurable lesions (including neck, chest, abdomen, and pelvis)
- Assessment of cardiac function and ejection fraction by two-dimensional echocardiography; abdominal color Doppler ultrasound, etc.

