# **8.4** Early Withdrawal (Discontinuation of Study Treatment)

### Three months after the Last Treatment:

- Physical examinations
- Vital signs measurements (body temperature, pulse, systolic and diastolic blood pressure, and respiratory rate)
- ECOG performance status
- Disease-related signs and symptoms
- Assessment and recording of AEs
- Hematology: Hemoglobin, ANC, WBC count, platelets
- Blood chemistry: Serum glucose, AST, ALT, total bilirubin, creatinine, Na, K, uric acid, total protein, and albumin
- Serum LDH
- Serum immunoglobulin quantification
- Urinalysis and stool
- Detection of LGLs in peripheral blood
- Detection of peripheral blood lymphocyte subsets (B/T/NK; Treg; T-cell immune function; TH1/TH2)
- Peripheral blood flow cytometry
- Peripheral blood TCRvβ flow cytometry
- Bone marrow smear, bone marrow biopsy, and immunohistochemistry
- Chromosome karyotype examination in bone marrow or peripheral blood
- ECG
- Evaluation of measurable lesions (including neck, chest, abdomen, and pelvis) by CT in patients with lymph node enlargement before admission
- Assessment of cardiac function and ejection fraction by two-dimensional echocardiography; abdominal color Doppler ultrasound, etc.
- Coagulation function

Following this assessment, patients will be followed up twice a year until the EOS, including survival, disease status, and long-term toxicity.

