# 9.2 Efficacy Evaluation

The evaluation will be started from Month 3. Hematologic ORR is defined as the sum of CR and PR.

Hematologic CR: Clinical symptoms and signs turn normal (splenomegaly disappears), and blood cell count completed turn normal, ie, hemoglobin >110 g/L, platelets >100 ×  $10^9$ /L, ANC >1.5 ×  $10^9$ /L, lymphocyte count <4 ×  $10^9$ /L, and LGLs in peripheral blood are within the normal range (<0.5 ×  $10^9$ /L).

Complete molecular response: No LGLs can be detected when reaching CR (negative TCR rearrangement by flow cytometry or polymerase chain reaction [PCR]).

Hematologic PR: Hematologic PR is defined as blood cell count that do not meet criteria for CR but improvement is observed, such as neutrophil counts  $>0.5 \times 10^9/L$  without repeated infection, an increase of hemoglobin level from baseline by more than 20 g/L without blood transfusion, platelets  $>50 \times 10^9/L$ .

SD: CR/PR criteria are not met after standardized treatment for 4 months, but no significant progression is observed.

PD: Cytopenia (hemoglobin decreased by 2 g/dL, <10 g/dL; ANC decreased by  $0.5 \times 10^9$ /L, <1.0 ×  $10^9$ /L; platelets decreased by  $20 \times 10^9$ /L, <100 ×  $10^9$ /L, requiring blood transfusion) or progressive worsening of organomegaly.

PFS: PFS is defined as the time from the first day of study to PD or death, including PD and death from any cause (eg, PD, toxicity, unrecorded progression in a new treatment, or death).

DoR: DoR is defined as the time when CR or PR is met until the first date of recurrent or progressive disease.

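### The planned growth modulation indices lack a valid denominator for many eligible patients: drop the DoR and OS ratios and limit the PFS ratio to documented prior progression

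*Supplement*

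**What the plan says.** Section 11.3 of protocol version 2.0, and the matching synopsis paragraph, commit the efficacy analysis to summarising "Growth modulation indices (intrasubject ratios of DOR, PFS, and OS, post-study treatment versus DOR, PFS, and OS post the most recent prior treatment regimen". No population, threshold or method is given for the ratios. The preceding sentence reads "The rules for DoR, PFS, and OS analyses will be specified in the Statistical Analysis Plan (SAP". No SAP is in the supplement. The component times on study "will be summarized descriptively using the Kaplan-Meier method".

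**Study line (numerator).** Section 4.1: "Efficacy evaluation will be conducted at the end of each cycle starting from Cycle 1", a cycle being 3 months. After treatment, Section 8.4 says "patients will be followed up twice a year until the EOS". Section 9.2 gives a numeric progression rule that starts "PD: Cytopenia (hemoglobin decreased by 2 g/dL, <10 g/dL" and adds limbs for neutrophils, platelets and organ enlargement. Section 4.4 caps follow-up at 24 months after treatment.

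**Prior line (denominator).** Section 5.2.1 admits treatment-naive as well as pretreated patients. Section 8 admits "patients with poor responses (failure to achieve PR) or relapse after receiving a non-methotrexate/thalidomide-based regimen", and also patients without PR within 4 weeks of methotrexate alone. Screening (Section 8.1) collects "Complete medical history (previous treatment and efficacy, enlargement of liver, spleen and lymph nodes; presence of other comorbidities". Section 9.2 starts DoR when CR or PR is met, and keeps SD distinct from PD.

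**The concern.** A within-patient ratio needs the same quantity, observed to its event, in both lines. Here the entry rules determine who has a denominator and how long it is. A patient who enters for lack of PR has a prior line that ended because treatment was judged insufficient, possibly after about a month, and not because the disease progressed. If that short time stands in for prior PFS, the ratio becomes large whatever the study regimen does. The DoR ratio does not exist for the same patient. The OS ratio compares a survival time with another that contains it.

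At stake is a descriptive efficacy result that could be read as each patient serving as their own control, in a single-arm trial with no other internal comparison.

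**Working it through.** The plan gives no figure for this index, so there is nothing to reproduce. The steps below compare the definitions with the entry rules and then size the effect under stated assumptions.

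**1. Which ratios exist for whom**

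| Route of entry | DoR ratio | PFS ratio | OS ratio |
|---|---|---|---|
| Treatment-naive | none | none | none |
| No PR on a prior regimen, or none within 4 weeks of methotrexate | none (no CR or PR to start from) | only if progression also occurred | prior death never observed |
| Relapse after response | exists if both dates are recorded | exists if the date is recorded | prior death never observed |

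**2. OS ratio.** Let P be the time from the start of the prior line to the start of study treatment, and S the survival time on study. Run to the same endpoint, the ratio is S/(P+S), which is always below 1. Cut at enrolment, it is S/P, which measures the spacing of two treatments. Illustration with P = 12 and S = 36 months: 36/48 = 0.75 or 36/12 = 3.0. Neither compares survival after two regimens.

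**3. PFS ratio with truncated prior lines, no treatment effect.** Assumptions, not in the documents: independent exponential PFS with a 24-month median on both lines, no censoring on study, and a fraction f of prior lines stopped at c months unless progression came first. A value of c near 1 corresponds to the 4-week methotrexate route; 6 is an assumed upper value. With q = 2^(−(1+r)c/24),

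P(ratio > r) = (1−f)/(1+r) + f·[(1−q)/(1+r) + q].

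The median is the r at which this equals 0.5. Check at f = 0.2, c = 6, r = 1.36: q = 0.664, and 0.339 + 0.2 × (0.142 + 0.664) = 0.500. Check at f = 0.6, c = 1, r = 9.27: q = 0.743, and 0.039 + 0.6 × (0.025 + 0.743) = 0.500.

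Restricted to documented prior progression,

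P(ratio > r) = [(1−f) + f(1−q)] / {(1+r)·[(1−f) + f(1−2^(−c/24))]}.

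| f | c (months) | Median ratio, truncated times used | Median ratio, documented progression only |
|---|---|---|---|
| 0.2 | 6 | 1.36 | 1.07 |
| 0.2 | 1 | 1.59 | 1.01 |
| 0.4 | 3 | 2.46 | 1.11 |
| 0.6 | 6 | 2.71 | 1.45 |
| 0.6 | 1 | 9.27 | 1.09 |

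The true median ratio is 1.00 throughout.

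**4. What the restriction does not cure.** If patients can enter only when the prior line failed within w months, then under the same null P(ratio > r) = (1−2^(−(1+r)w/24)) / [(1+r)(1−2^(−w/24))]. The median is 1.00 with no window, 1.39 for w = 60, 2.7 for w = 24 and 5.0 for w = 12. The protocol states no window, so this is a range and not an estimate.

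**5. Censoring on study, no treatment effect.** Simulation of 400,000 pairs, censoring uniform over 24 to 48 months, no entry window:

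| Median PFS, both lines (months) | Censored | Median ratio, censored times as observed | Events only | Kaplan-Meier on the ratio |
|---|---|---|---|---|
| 12 | 13% | 0.96 | 0.78 | 1.03 |
| 24 | 36% | 0.78 | 0.51 | 1.25 |
| 36 | 51% | 0.64 | 0.37 | 1.77 |

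Kaplan-Meier on the ratio runs high because the ratio and its censoring limit share a denominator, so censoring is informative. With a real effect and a prior median of 12 months, it gives 2.55 for a true 2.0 and 5.3 for a true 3.0.

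**6. Assessment interval.** If the study line is read 3-monthly, the null median ratio is 0.95 with a 6-monthly prior line and 1.06 with a monthly one. This is minor.

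**The case against.** A reader might infer more than the documents support, in three ways.

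- **That every prior line is a fully observed failure under routine care.** Section 8 contradicts the first part, since lack of PR is enough for entry and Section 9.2 does not count that as progression. Routine care is a reasonable inference, but it is not stated.
- **That the index is biased by construction.** Selection on failure alone leaves the null median at 1.00 if every patient eventually fails and enters. The inflated values in step 4 need an entry window that appears nowhere in the protocol. Early-failure selection pushes the ratio up, while censored times used as observed push it down, so no net direction is established.
- **That the missing rule for censored numerators is itself a fault.** Section 11.3 leaves the rules for the component endpoints to the SAP, which is not in the supplement. Nothing shows that censored times would be treated as events or dropped.

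It can also fairly be said that the index is one descriptive clause. It is not among the objectives in Section 3 or the endpoints in Section 9.3, has no test or threshold, and applies only to pretreated patients.

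All of this stands and lowers the weight of the point. It does not supply the missing denominators: rules for DoR, PFS and OS on study cannot create a prior DoR for a non-responder or a prior death for a living patient.

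**Conclusion.** The point holds at low severity. The DoR ratio is undefined for patients who entered without a prior response. The OS ratio has no meaningful denominator for anyone. The PFS ratio is interpretable only where prior progression is documented. Using truncated prior times could give a null median ratio of 1.4 to 9.3, against 1.0 to 1.45 with the restriction. Both ranges rest on assumed 24-month exponential PFS and on an assumed 20% to 60% of prior lines cut at 1 to 6 months; the documents give neither PFS medians nor the expected mix of entry routes.

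Even when restricted, the ratio sets a scheduled study line against a prior line selected for poor outcome and drawn from medical history. The sign and size of the remaining bias depend on entry timing and censoring. The CRR analysis and its sample size are untouched.

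**What to change.** In Section 11.3 and the synopsis:

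- Delete the DoR and OS ratios.
- Restrict the PFS ratio to pretreated patients with a documented progression date on the most recent prior regimen. Define prior PFS from the first day of that regimen, and date progression by the Section 9.2 criteria where past counts exist.
- State how many pretreated patients are left out and why.
- Do not apply Kaplan-Meier to the ratio. List the paired times with censoring marked, and report the proportion above a cut fixed in advance. Give a lower bound that counts patients censored below the cut as not exceeding it, and an upper bound that counts them as exceeding it.
- Label the result exploratory, and state that prior lines were selected for poor outcome and taken from history.

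The cost is protocol and SAP wording, plus abstraction of past counts where they are available. The result will rest on fewer patients and will probably look less favourable.
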